Comparison of Therapeutic Effects of Greater Occipital Nerve Blockade, Topiramate and Flunarazine in Episodic Migraine

07.07.2019

Objective: The preventive drug therapy in migraine is for reducing the attack frequency, severity and duration of the headache. Flunarizine and topiramate are widely used in the prevention of migraine attacks. Greater occipital nerve block (GONB) is an alternative treatment option which is used in the prophylactic treatment of migraine. In this study we compared the effectiveness of GONB, topiramate and flunarizine by means of reduction in post treatment VAS scores and attack frequencies in episodic migraine patients in a one month period.

Material and Methods: One hundred and twenty migraine patients were aimed to be divided into three treatment groups namely flunarazine, topiramate and GONB. Patients were followed for 4 weeks and attack frequencies and VAS scores were recorded weekly. At the end of fourth week, response rates, rates of 50% and 75% or more reduction in VAS and attack frequencies were calculated. Groups wise comparisons were assessed statistically.

Treatment protocol

Flunarizine was introduced with a single dose of 10 mg/day. Topiramate was administered twice a day at a dose of 25 mg/day, which was increased to 100 mg/day in the second week. The GONB solution was prepared with 1 ml triamcinolone (40mg), 2 ml bupivacaine (10 mg), and 1 ml 0,9% NaCl. The solution was administered using a 22G × 1¼" (0.7 × 40mm) injector with the patient lying prone on the table. Injection was applied to medial of the occipital artery localized at the medial one-third of the superior nuchal line between the occipital tubercle and

mastoid process. The scalp was cleaned with iodine before the procedure, and the injections were performed bilaterally at a volume of 2 mL after negative aspiration for blood.

Statistical analysis

Normality of distribution was assessed with the D'Agostino-Pearson test. Continuous variables with a normal distribution were assessed in two or more groups using the Student's t-test and ANOVA test, respectively. Non-parametric counterparts of these tests (Mann Whitney U and Kruskal-Wallis tests) were utilized to compare the data that were not normally distributed. Nominal categorical data were assessed using the chi-square test. The pre- and post-treatment comparison of normally and non-normally distributed data were undertaken using the paired t-test and the Wilcoxon test, respectively. A two-tailed p value of <0.05 was considered to be statistically significant.

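### No between-arm test adjusts for the pre-treatment value as a covariate; if allocation is random, adjustment would sharpen the VAS comparison at almost no cost, but the plan does not state the allocation method

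*Combined protocol and SAP*

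**What the plan says.** The Objective sets out to compare the effectiveness of the three treatments "by means of reduction in post treatment VAS scores and attack frequencies in episodic migraine patients" over one month. On how patients reach an arm, Material and Methods offers one sentence: "One hundred and twenty migraine patients were aimed to be divided into three treatment groups namely flunarazine, topiramate and GONB". It gives no method, ratio or sequence.

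The week-4 outcomes are listed as follows: "At the end of fourth week, response rates, rates of 50% and 75% or more reduction in VAS and attack frequencies were calculated". The comparison itself is described only as "Groups wise comparisons were assessed statistically".

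Statistical analysis then names the tests:

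- Normal continuous data: "Continuous variables with a normal distribution were assessed in two or more groups" by Student's t-test and ANOVA.
- Non-normal continuous data: "Non-parametric counterparts of these tests (Mann Whitney U and Kruskal-Wallis tests) were utilized to compare the data that were not normally distributed".
- Categorical data: "Nominal categorical data were assessed using the chi-square test".
- Within patients over time: "The pre- and post-treatment comparison of normally and non-normally distributed data were undertaken using the paired t-test and the Wilcoxon test, respectively".

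Only the last item names pre-treatment data, and it compares before with after, not arm with arm.

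**The concern.** A reduction, a 50% or 75% reduction rate and a paired pre/post test all need an earlier value, so pre-treatment VAS and attack frequency must be available. Yet they enter the between-arm comparisons at most through the definition of a reduction. No named test holds the pre-treatment value constant when arms are compared.

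What this costs depends on two things the plan does not say.

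- **Allocation.** If it is random, leaving out the covariate loses precision but not validity. If it is not random, arms may differ before treatment, and the choice between a change score and an adjusted score can decide whether a difference appears at all.
- **The continuous outcome.** The gain from adjustment is different against a change score and against a week-4 score.

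**Working it through.** **Inputs.** From the documents: 120 patients in three groups, and a two-sided 0.05 significance level. Assumed, because the documents do not give them: an equal split (120/3 = 40 per arm), equal pre and post SDs, a pre/post correlation r of 0.3, 0.5 or 0.7, and a true difference of 0.5 SD in one arm. The target of 120 comes without an effect size, SD or power, so there is no planned figure to reproduce.

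**1. Variance under random allocation.** In units of the raw-score SD squared, the per-patient variance behind a between-arm difference is 1 for a week-4 score, 2(1 − r) for a change score and 1 − r² for ANCOVA. Hence:

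- ANCOVA/change = (1 − r²)/[2(1 − r)] = (1 + r)/2 = 0.65, 0.75, 0.85.
- ANCOVA/week-4 = 1 − r² = 0.91, 0.75, 0.51.

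The gain shrinks as r rises in the first comparison and grows in the second.

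**2. Three-arm power.** With arm means (0, 0, 0.5), the sum of squared deviations from their mean is 0.1667. The noncentrality is 40 × 0.1667 / variance factor, which gives 6.67 for week-4 scores. For change it is 4.76, 6.67 and 11.11; for ANCOVA it is 7.33, 8.89 and 13.07. The F test has 2 and 117 df unadjusted, and 2 and 116 df with the covariate.

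**3. Pairwise detectable difference.** Noncentral t, 80% power, 78 df unadjusted and 77 df adjusted.

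| r | Power: change | Power: week-4 | Power: ANCOVA | Detectable SD: change | Detectable SD: week-4 | Detectable SD: ANCOVA |
|---|---|---|---|---|---|---|
| 0.3 | 47% | 62% | 66% | 0.75 | 0.63 | 0.61 |
| 0.5 | 62% | 62% | 75% | 0.63 | 0.63 | 0.55 |
| 0.7 | 85% | 62% | 90% | 0.49 | 0.63 | 0.45 |

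**4. Sensitivity to equal SDs.** Let k be the post/pre SD ratio. The ANCOVA/change ratio becomes k²(1 − r²)/(1 + k² − 2rk). At r = 0.5:

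- k = 0.5: 0.1875/0.75 = 0.25
- k = 1: 0.75/1 = 0.75
- k = 1.5: 1.6875/1.75 = 0.96

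**5. Non-random allocation with no treatment effect.** Take two arms of 40 that differ by d = 0.5 SD before treatment, with r = 0.5. Rejection rates come from 40,000 simulated trials per setting.

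- If the difference is a stable one in severity, the change score is unbiased and ANCOVA shows a spurious d(1 − r) = 0.5 × 0.5 = 0.25 SD. The change test rejects 5% of the time and ANCOVA 23%.
- If patients were selected on the observed pre-treatment value, the change score shows the spurious 0.25 SD and ANCOVA is unbiased. The change test rejects 20% of the time and ANCOVA 5%.

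The two methods swap places, so neither is safe until the route into each arm is known.

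**The case against.** Several objections have force.

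- **Baseline is used.** A reader might infer that the between-arm tests ignore pre-treatment values altogether. The documents do not support that: a chi-square test on 50% or 75% reduction rates, or an ANOVA on reductions, uses the earlier value through the outcome. What is absent is covariate adjustment.
- **A change-score test is not stated.** It is tempting to read the gain from 47% to 66% power at r = 0.3 as the loss in the plan. Statistical analysis never says that changes are what the continuous tests compare. If week-4 scores are meant, the same case goes only from 62% to 66%.
- **The figures cover VAS only.** The outcomes that Material and Methods explicitly calculates at week 4 are rates. The precision argument is for a roughly normal continuous score. It is not claimed for responder rates, where an adjusted odds ratio is a different, conditional quantity and need not be more precise, or for attack counts.
- **Unadjusted tests are valid under randomisation.** This is correct, and it makes adjustment a matter of efficiency, not a correction of an error.
- **Silence on allocation is not evidence of non-random allocation.** Equally, it does not follow that no difference could ever be credited to treatment. The supportable statement is that, without randomisation, neither comparison can do so by itself.

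These points limit the size and reach of the gain. They do not remove it for VAS: under the equal-SD assumption ANCOVA has the smaller variance than either alternative at every r examined, and the data it needs are already required by the plan.

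**Conclusion.** The point holds in a limited form. No named between-arm test adjusts for the pre-treatment value, and the plan states neither the allocation method nor whether continuous comparisons use week-4 values or changes. If allocation is random, ANCOVA is the better main comparison for VAS. Under the assumptions listed, power for one arm 0.5 SD apart becomes 66%, 75% or 90%, against 47%, 62% or 85% for change scores and 62% for week-4 scores. The exact gain is not established, because r, the SD ratio and the split are not in the documents; the SD ratio alone moves the ANCOVA/change variance ratio from 0.25 to 0.96 at r = 0.5. If allocation is not random, adjustment does not rescue the comparison. The illustrations of that case rest on a chosen 0.5 SD imbalance and two simple mechanisms. This is a change that should be made, not a fatal flaw.

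**What to change.** 1. State how the 120 patients are allocated to the three arms, and define the pre-treatment reference used for reductions and for adjustment.
2. If allocation is random, compare arms on week-4 VAS by ANCOVA with pre-treatment VAS as covariate, and on attack frequency by a count model with pre-treatment frequency as covariate. Keep the 50% and 75% responder comparisons as planned outcomes. Keep the unadjusted and rank-based tests as sensitivity analyses, including when VAS is not normally distributed.
3. If allocation is not random, say how treatment was chosen, report both the change-score and the baseline-adjusted comparison, and word the conclusion as an association.

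The cost is slightly more analysis work, with a model in place of a simple test; no extra patients, visits or data are needed. The document is written in the past tense, so if outcome data have already been seen, the adjusted analysis must be labelled post hoc. In the non-random case the price is a more cautious conclusion.

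### Weekly VAS and attack records are collected, but the value to be analysed is undefined, week 4 alone is permitted, and no named analysis uses all four weeks or adjusts for baseline

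*Combined protocol and SAP*

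**What the plan says.** Material and Methods sets the schedule: "Patients were followed for 4 weeks and attack frequencies and VAS scores were recorded weekly". The derived outcomes follow: "At the end of fourth week, response rates, rates of 50% and 75% or more reduction in VAS and attack frequencies were calculated". The Objective frames the comparison as "reduction in post treatment VAS scores and attack frequencies in episodic migraine patients in a one month period".

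The Statistical analysis section gives the between-arm tests: "Continuous variables with a normal distribution were assessed in two or more groups using the Student's t-test and ANOVA test, respectively". Mann-Whitney U and Kruskal-Wallis replace these when data are not normal, and chi-square is used for categorical outcomes. Paired t and Wilcoxon tests serve the comparison before and after treatment. No mixed model, count model or covariate-adjusted model appears, and neither the post-treatment window nor the baseline window is defined.

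On size, "One hundred and twenty migraine patients were aimed to be divided into three treatment groups". No allocation ratio, power, effect size, standard deviation or dropout rate is given. The threshold is: "A two-tailed p value of <0.05 was considered to be statistically significant".

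**The concern.** Up to four post-treatment records per patient are available, but each listed test accepts one number, or one before/after pair. The plan never says how four become one. Baseline must exist, because percentage reductions and paired tests need it. In the between-arm tests, though, it can enter only inside a derived change or percentage, never as a covariate.

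Two things are at stake. The first is precision. With about 40 patients per arm and three active treatments, there is little to spare, and a single week's attack count in episodic migraine is small and noisy. The second is prespecification. Readings of the same sentence differ widely in precision and, if effects change over time, in what they estimate. An analyst could choose among them after seeing the data.

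**Working it through.** **1. Sample size.** The stated 120 cannot be reproduced, because no inputs are given. Equal allocation is assumed: 120/3 = 40 per arm. For orientation, 80% power at two-sided 0.05 for one pairwise comparison needs a difference of (1.96 + 0.84) × √(2/40) = 0.63 SD.

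**2. Attack counts, constant effect.** All rates here are assumptions. Weekly counts are gamma-Poisson, with a baseline mean of 6 per 4 weeks, between-patient CV 0.5 and response CV 0.4. True reductions are 40% and 60%, the same in every week, with 40 per arm and 2000 simulated trials per scenario. Null rejection was 4–6% for all methods.

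| Analysis | Week 4 only | Weeks 1–4 total |
|---|---|---|
| 50% responder, chi-square | 20% | 40% |
| Rank test on counts | 23% | 49% |
| Baseline-adjusted total | – | 53% |

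Like for like, week 4 keeps 20/40 = 0.50 or 23/49 = 0.47 of the power. For baseline means of 4 to 8, week-4 responder power is 16–26% and adjusted-total power is 44–61%. In this model 94% of week-4 counts are 0, 1 or 2, and the 50% and 75% classifications agree in about 90% of patients, so on a week-4 basis the second threshold adds little.

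**3. VAS, constant effect.** Assume weekly SD 1, one baseline value and the same correlation r between any two measurements. The variance multipliers V are:
- week-4 change: 2(1 − r)
- change to the four-week mean: 1.25(1 − r)
- week-4 ANCOVA: 1 − r²
- ANCOVA on the four-week mean: (1 + 3r)/4 − r²

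Power is approximately Φ(d/√(2V/40) − 1.96). At r = 0.5 and d = 0.5:

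| Analysis | V | d/√(2V/40) | Power |
|---|---|---|---|
| Week-4 change | 1.000 | 2.236 | 61% |
| Change to 4-week mean | 0.625 | 2.828 | 81% |
| Week-4 ANCOVA | 0.750 | 2.582 | 73% |
| ANCOVA on 4-week mean | 0.375 | 3.651 | 95.5% |

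For change scores the variance ratio is 1.25/2 = 0.625 at any r. Over r = 0.3–0.8 and d = 0.2–0.8, week 4 alone keeps 0.68–1.00 of the power for change scores and 0.50–1.00 for ANCOVA.

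**4. Effect that builds up.** The Treatment protocol changes the topiramate dose in the second week, so a constant effect cannot be taken for granted. Assume 25/50/75/100% of the full effect in weeks 1–4; the mean effect is then 0.625d.
- VAS at r = 0.5, d = 0.5: change to the four-week mean falls to 42% (week-4 change: 61%), and ANCOVA on the mean to 63% (week-4 ANCOVA: 73%).
- Attacks, build-up in both arms: week-4 rank test 24%, four-week total 16%, adjusted total 18%. With build-up in the better arm only: 24%, 6% and 5%.
- Attacks, half effect in week 1 and full effect afterwards: the adjusted total has 38%. This is still above the 23% of the week-4 rank test, though baseline adjustment explains part of that gap.

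**The case against.** The strongest reply is that the plan may already use all four weeks. The sentence on response rates says when they were computed, not which records went into them, and a one-month comparison fits a monthly total naturally. A sum is one value per patient, yet it discards no week. In that case the remaining gain for attacks is only from 49% to 53%. This stands. A reader might infer that the plan reduces the data to a single week-4 value, but the documents do not say so. They leave the value open.

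Second, averaging over weeks 1–4 is partly a choice of question, and with a slow build-up it does worse. That also stands, and it is why a week-4 contrast must accompany the average.

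Third, the remedy needs things the documents do not describe: a baseline count on a matching time scale, and a rule for VAS in weeks without an attack. Under the simulated assumptions about 47% and 59% of patient-weeks in the two arms are attack-free, so this is a practical matter, and the VAS formulas above do not simply carry over if those weeks are missing or set to zero. This limits the VAS figures. It does not remove the need to define the outcome.

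**Conclusion.** The concern holds in a limited form. The documents establish that the records are weekly, that the between-arm tests take one value per patient without baseline adjustment, that no named analysis uses the four records together, and that week 4 alone is a permitted reading.

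The size of the loss is conditional. If week 4 alone is used and the effect is constant over weeks, power for attacks is roughly half that of the four-week total under the stated assumptions. If the total is already intended, the loss is near zero. If the effect builds slowly, the ordering can reverse.

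A reader might also infer that the plan forfeits up to half its power. The documents give no attack rates, standard deviations or correlations from which such a figure could come, and it is not a bound. Setting a week-4 responder test (20%) against an adjusted total (53%) exceeds it, but mixes the window, dichotomisation and baseline adjustment. For VAS change scores the window alone costs at most about 32% of power (ratio 0.68), and almost nothing when power is already high. Nor would the better analysis rescue the trial by itself: 53% is still modest, for an assumed effect.

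**What to change.** Amend the Statistical analysis section as follows.

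- **Attacks.** To match the one-month objective, define the outcome as the total over weeks 1–4, against a baseline count on the same time scale. Compare arms with a negative binomial model with arm and log baseline count, and state the allowance for zero counts. Confirm that the baseline is recorded over a usable window.
- **VAS.** Compare arms with a repeated-measures model with arm, week, arm-by-week and baseline VAS. Prespecify the average contrast over weeks 1–4, and report the week-4 contrast alongside it. State how VAS is handled in attack-free weeks.
- **Response rates.** Compute the 50% and 75% attack response rates on the four-week totals, state the window for the VAS rates too, and keep all of them secondary.

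The cost is plan wording and slightly more analysis work. No extra patients or visits are needed, provided the baseline count covers a suitable period. The downside is that a four-week average gives less weight to a late-building effect. The week-4 contrast covers this for VAS; for attacks, the choice of window should be stated as deliberate.

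### VAS is judged by pre/post tests and 50%/75% reduction rates, but nothing puts the pre-treatment and follow-up VAS on the same footing; a baseline-adjusted comparison between arms should carry the VAS result

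*Combined protocol and SAP*

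**What the plan says.** The Objective compares the three treatments "by means of reduction in post treatment VAS scores and attack frequencies in episodic migraine patients in a one month period", so VAS and attack frequency are two separate measures. Material and Methods gives the only recording schedule: "Patients were followed for 4 weeks and attack frequencies and VAS scores were recorded weekly". It then defines the responder outcomes: "At the end of fourth week, response rates, rates of 50% and 75% or more reduction in VAS and attack frequencies were calculated".

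Under Statistical analysis, change within an arm is tested as follows: "The pre- and post-treatment comparison of normally and non-normally distributed data were undertaken using the paired t-test and the Wilcoxon test, respectively". Arms are compared by ANOVA or Kruskal-Wallis for continuous data. For rates, "Nominal categorical data were assessed using the chi-square test". No baseline adjustment is mentioned.

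Three items are not stated anywhere:
- how, and over what period, the pre-treatment VAS was obtained;
- what VAS is entered for a week without an attack;
- whether the post-treatment value is the week-4 score or a summary of the four weeks.

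**The concern.** A percent reduction, or a paired difference, means something only if its two ends are measured by the same rule. In episodic migraine some weeks pass without an attack, treated or not. If the pre-treatment VAS is a rating of a usual attack, it cannot reflect such weeks, whereas a weekly follow-up score can. Entering 0 for those weeks would then turn ordinary gaps between attacks into a VAS reduction.

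All three arms are active treatments, so no arm would show how much of a pre/post change is artefact. Each arm could report a significant VAS fall and a 75% response rate that need no treatment effect. The VAS rate would also partly repeat attack frequency.

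**Working it through.** The plan gives no power or VAS figure to reproduce, so the check has two parts: arithmetic on single records, and a no-effect calculation with assumed inputs.

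**Single records (no attack rate assumed)**

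Patient A: attack VAS 8 before and after treatment, one attack in each of weeks 1-3, none in week 4. Nothing has changed.
- Week 4 scored 0: 1 − 0/8 = 100% reduction, a 75% responder.
- Four-week mean with 0: (8+8+8+0)/4 = 6, so 1 − 6/8 = 25%.
- Attack weeks only: mean 8, so 0%.

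Patient B: baseline 8, weeks 1-2 scored 8 and 6, no attack in weeks 3-4.
- Week 4 with attack-free weeks left out: no value.
- Attack weeks only: 1 − 7/8 = 12.5%.
- Four-week mean with 0: (8+6+0+0)/4 = 3.5, so 1 − 3.5/8 = 56%.
- Week 4 scored 0: 100%.

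All four results are compatible with the text.

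**No-effect calculation**

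From the document: 120 patients in three groups, hence 120/3 = 40 per arm if allocation is equal (the ratio is not stated), and two-sided 0.05. Assumed: attacks Poisson at the same rate before and after; attack VAS mean 7.5, between-patient SD 1.0, per-attack SD 1.5; baseline a usual-attack rating; attack-free weeks scored 0. With m attacks per four weeks, P(attack-free week) = exp(−m/4).

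| Attacks per 4 weeks | 4 | 6 | 8 |
|---|---|---|---|
| P(attack-free week) | 37% | 22% | 14% |
| Week 4: false 75% responders | 37% | 22% | 14% |
| Week 4: paired t rejects | 100% | 92% | 63% |
| 4-week mean: false 50% responders | 31% | 13% | 5% |
| 4-week mean: false 75% responders | 8% | 2% | 0.5% |
| 4-week mean: paired t rejects | 100% | 100% | 99% |
| Same zero rule over four baseline weeks | 4.6% | 4.9% | 5.1% |
| Attack weeks only | 5.2% | 4.7% | 5.0% |

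The last two rows are paired t rejection on the four-week value.

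Hand check at 6 per month, week 4 (per-attack SD 1): mean apparent fall 7.5 × 0.223 = 1.67; SD of the difference about 3.37; SE 3.37/√40 = 0.533; t = 1.67/0.533, about 3.1; rejection about 87%, against 90.5% simulated with that SD.

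With fixed-count, Poisson and gamma-Poisson (shape 2) attack timing, and per-attack SD 1, the week-4 paired t-test rejects in 39% to 100% over 4 to 8 attacks per month. The artefact shrinks as attacks become more frequent: at 12 per month under Poisson timing it rejects in 13% (week 4) and 39% (4-week mean).

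**Between two arms** (40 each, 6 attacks per month, Poisson and gamma-Poisson)

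- Same per-attack VAS effect, frequency reduced 55% in both: chi-square on the 50% VAS rate, zero-scored, rejects in 5%.
- Same per-attack VAS effect, frequency reduced 40% vs 70%: zero-scored ANCOVA rejects in 73%-88%; ANCOVA on attack weeks only, about 5%.
- Severity alone differs (post/pre ratio 0.75 vs 0.55): chi-square on the zero-scored 50% rate 25%-34%; zero-scored ANCOVA 39%-48%; ANCOVA on attack weeks only 82%-88%.

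**Patients lost when only attack weeks count** (P of no attack in four weeks, from 6 per month)

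- No effect: exp(−6) = 0.2% (Poisson) or (1+6/2)^−2 = 6.25% (gamma-Poisson), so 0.1 to 2.5 of 40.
- Frequency down 40%, mean 3.6: exp(−3.6) = 2.7% or 2.8^−2 = 12.8%, so 1.1 to 5.1 of 40.
- Frequency down 70%, mean 1.8: exp(−1.8) = 16.5% or 1.9^−2 = 27.7%, so 6.6 to 11.1 of 40.

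**The case against.** The inflation needs two choices together: attack-free weeks scored 0, and a baseline not diluted by attack-free weeks. The document makes neither. It is a short summary, and its silence is not evidence that the rules differ. The planned percent reduction in attack frequency also implies some pre-treatment period, so a matching VAS record may exist. If the VAS instead rates usual attacks whatever happened that week, the problem does not arise. All of this stands. A reader might infer that the within-arm VAS results are biased; the text supports only that they could be, under one permitted reading.

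A reader might also infer that comparisons between arms are inflated. They are not when frequency falls equally. When it does not, zero scoring detects a real difference in prevention and labels it VAS: a labelling fault, not a false positive.

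A zero-scored composite as the main VAS outcome would make that fault worse, as the 73%-88% figure shows. Leaving attack-free weeks out has its own weakness, because patients who respond completely drop out, and more of them from the better arm.

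What the objection does not remove is that a reader cannot tell which rule applies, and the permitted rules run from about 5% rejection to near certainty.

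**Conclusion.** The point holds as a conditional weakness. The within-arm paired tests and the absolute 50%/75% VAS rates cannot be read as evidence of effect unless the pre-treatment and follow-up VAS follow one rule, and the plan provides none. Under zero scoring against a usual-attack baseline, the week-4 paired t-test rejects in roughly 40% to 100% of arms with no effect. Under a matched rule, or with attack weeks only, it rejects in about 5%. The size rests on assumed attack rates (4 to 8 per month), an assumed VAS distribution and equal allocation; the direction does not.

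Separately from the scoring question, the planned comparison of arms is weaker than it need be. With the same zero-scored data, chi-square on the 50% rate finds a severity-only difference in 25%-34% of trials, against 39%-48% for baseline-adjusted ANCOVA.

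**What to change.** 1. Make the main VAS comparison an ANCOVA between arms on the weeks 1-4 VAS, adjusted for pre-treatment VAS and pre-treatment attack frequency. It replaces the unadjusted ANOVA/Kruskal-Wallis tests and the chi-square tests on 50%/75% VAS rates; give those rates descriptively. ANCOVA does not need the baseline to be on the same scale as the outcome.
2. Score VAS as severity, from weeks with a recorded attack only. A week with no record is missing, not attack-free. Analyse attack frequency separately, and report per arm how many patients had no attack in the four weeks.
3. State how the pre-treatment VAS was obtained and apply the same rule to it. If the rules differ, do not read the within-arm paired tests as evidence of effect. If the VAS rates usual attacks regardless of the week, say so.
4. A zero-scored four-week mean may be given as a sensitivity analysis, labelled as severity and frequency combined.

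**Cost.** No new data should be needed: weekly attack counts identify attack-free weeks, and the planned pre/post and percent-reduction analyses already require both pre-treatment values. The real price is the loss of attack-free patients from the VAS analysis, up to about 11 of 40 in the example with a 70% frequency reduction. That loss is unequal between arms if the treatments differ in prevention. The 5% level shown for attack-week scoring also assumes that severity is unrelated to whether attacks stop, so the VAS result must be read beside the frequency result.

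### No between-arm test adjusts for baseline VAS or baseline attack frequency, so the three-way comparison gives up precision that data already in hand could supply

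*Combined protocol and SAP*

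**What the plan says.** The Objective sets out a comparison of three treatments "by means of reduction in post treatment VAS scores and attack frequencies in episodic migraine patients in a one month period". Under Material and Methods, "One hundred and twenty migraine patients were aimed to be divided into three treatment groups". On data collection it says: "Patients were followed for 4 weeks and attack frequencies and VAS scores were recorded weekly".

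The Statistical analysis section gives the between-arm tests for continuous data: "Continuous variables with a normal distribution were assessed in two or more groups", by Student's t-test for two groups and ANOVA for more. It continues: "Non-parametric counterparts of these tests (Mann Whitney U and Kruskal-Wallis tests) were utilized to compare the data that were not normally distributed". Responder rates (50% and 75% or more reduction) fall under the chi-square test.

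Pre-treatment values appear in that section only within arms: "The pre- and post-treatment comparison of normally and non-normally distributed data were undertaken using the paired t-test and the Wilcoxon test, respectively".

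No ANCOVA, regression, mixed model or stratified test is named. The section does not say whether the between-arm tests are run on post-treatment values or on reductions. Baseline recording is not described as such, but neither a reduction nor a pre/post test can be computed without it.

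**The concern.** With about 40 patients per arm, how much can be learned about differences between arms depends heavily on the residual variance. VAS and attack frequency before treatment would normally be expected to predict the same measures afterwards. A test that ignores this leaves the predictable part of the outcome in the error term.

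Testing raw reductions does not cure the problem. Subtracting baseline fixes its coefficient at 1, whereas ANCOVA estimates it. When the pre/post correlation is modest, subtraction adds noise.

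Both unadjusted choices also leave chance baseline imbalance in the contrast. A post-treatment comparison carries it in one direction and a change comparison in the other. What is at stake is wider intervals, lower power and some exposure to unlucky allocation. Under random allocation the 5% error rate, averaged over allocations, is not affected.

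**Working it through.** **Inputs from the documents.** 120 patients, three arms, two-sided 0.05. The plan gives no effect size, SD or power, so its sample size cannot be reproduced.

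**Assumptions.** Equal split (120 / 3 = 40 per arm), random allocation, equal pre and post variances, and pre/post correlation r, which the documents do not give and which is therefore varied.

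**VAS: variance of an arm difference**, in units of SD² × 2/40:

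- post-treatment values only: 1
- raw change: 2(1 − r)
- ANCOVA: (1 − r²) × [1 + 1/(120 − 3 − 2)] = (1 − r²) × 1.0087, where the last factor is the cost of one covariate

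Before that cost, the ratio of ANCOVA to post-only is 1 − r², and of ANCOVA to change is (1 − r²)/[2(1 − r)] = (1 + r)/2. Both are below 1 for every r between 0 and 1.

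The 95% half-width is t(0.975) × √(2/40 × v), with v the relevant variance above, on 117 df (unadjusted) or 116 df (ANCOVA). For example, ANCOVA at r = 0.5 has v = 0.75 × 1.0087 = 0.757, and 1.98 × √(0.05 × 0.757) = 0.39 SD. Power is from the noncentral t at an illustrative difference of 0.5 SD.

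| r | Net variance cut vs post-only | Net variance cut vs change | Half-width (SD): post / change / ANCOVA | Power: post / change / ANCOVA |
|---|---|---|---|---|
| 0.1 | 0.1% | 45% | 0.44 / 0.59 / 0.44 | 60% / 38% / 60% |
| 0.3 | 8% | 34% | 0.44 / 0.52 / 0.42 | 60% / 47% / 64% |
| 0.5 | 24% | 24% | 0.44 / 0.44 / 0.39 | 60% / 60% / 72% |
| 0.7 | 49% | 14% | 0.44 / 0.34 / 0.32 | 60% / 82% / 87% |
| 0.9 | 81% | 4% | 0.44 / 0.20 / 0.19 | 60% / 99.9% / 99.9% |

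A simulation of 20,000 three-arm trials gave variance cuts of 8%, 25% and 48% against post-only and 35%, 24% and 14% against change at r = 0.3, 0.5 and 0.7, in agreement with the formulas. At r = 0.5, before the covariate cost, 40 × 0.75 = 30 adjusted patients per arm match 40 unadjusted.

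**Chance imbalance.** A baseline gap of 2 SE or more arises in about 4.5% of single pairs (P(|Z| ≥ 2)) and in 11% of three-arm trials for at least one pair (1,000,000 draws). A 2-SE gap is 2 × √(2/40) = 0.447 SD at baseline. It moves the post-only contrast by r × 0.447 = 0.13, 0.22 or 0.31 SD at r = 0.3, 0.5 or 0.7. It moves the change contrast by (r − 1) × 0.447 = −0.31, −0.22 or −0.13 SD.

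**Attack counts, by simulation only.** Every figure here rests on an assumed set-up: 40 per arm, a mean of 5 attacks per 4 weeks at baseline, a 40% fall (mean 3), a gamma-distributed patient effect shared by both periods (shape 20, 6, 2.5 or 1) and a separate gamma effect in each period (shape 10). There were 1,000 to 1,500 runs per setting.

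- Adding log(baseline count + 0.5) to a negative binomial model cut the variance of the log rate ratio by about 0%, 7%, 25% and 46% at count correlations of 0.12, 0.30, 0.50 and 0.68. Repeat runs near 0.3 and 0.5 gave 6–7% and 20–28%.
- Power at a rate ratio of 0.7 was 47% (Mann-Whitney on post counts), 51% (unadjusted model) and 54% (adjusted model) at correlation 0.30. At 0.50 it was 33%, 40% and 46%.
- So adjustment itself accounts for 3 of 7 points at 0.30 and 6 of 13 at 0.50. The remainder comes from using a count model.

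**The case against.** The strongest reply is that this concerns efficiency and is not an error. Under random allocation the planned tests are legitimate and keep their 5% level. That stands.

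The size of the loss is not anchored in the documents. If r is about 0.1 or less there is nothing to gain over post-treatment values, and if r is near 0.9 almost nothing over change. The Objective speaks of reductions, which suggests change is the intended scale. The largest figures, those against post-only at r = 0.7, would then not apply. All of that is fair, and it is why both comparators and a wide range of r are shown. It does not reverse the conclusion: at worst, at r near 0, adjustment costs about 0.9% in variance, and for most plausible r it helps whichever scale is meant.

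The count evidence is weaker. It depends on invented event rates, and the adjusted test ran at 5.3–6.5% in the main simulations (4–5% in a repeat), so the power comparison with Mann-Whitney is not exactly size-matched. It should be read as showing the direction and rough size of the gain.

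No primary outcome is named. If the responder rates carry the conclusion, adjusting VAS and counts does not touch it. That is a limit on the reach of the fix.

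Finally, allocation is described only as dividing patients into groups. If it was not random, that is the larger problem, and a baseline covariate does not remove confounding by other factors.

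**Conclusion.** The concern holds. Every between-arm test in the plan is unadjusted, baseline values must be available, and for VAS the adjusted analysis is more precise than either unadjusted reading once r is above about 0.1 and short of about 0.98, where (1 + r)/2 × 1.0087 reaches 1. At r = 0.5 the gain is a 24% net cut in variance and 12 points of power for a 0.5 SD difference (60% to 72%). These sizes rest on 40 per arm, equal variances, random allocation and assumed correlations. They are computed for the t-test and ANCOVA; for VAS the rank tests were not evaluated. The count figures are indicative only.

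This is a change the sponsor should make. Its absence does not invalidate the planned tests. Confidence in the size of the gain is medium, because the correlation is unknown.

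**What to change.** - **VAS:** make the main between-arm analysis an ANCOVA of week-4 VAS on arm and baseline VAS.
- **Attacks:** make it a negative binomial regression of the total 4-week count on arm and log(baseline count + 0.5). The added 0.5 allows for zero baseline counts, which occurred in 2–18% of simulated patients. Take the baseline count over a stated pre-treatment period.
- **Reporting:** give the three pairwise adjusted differences or rate ratios with 95% confidence intervals.
- **Supportive analyses:** keep the planned t-test/ANOVA and rank tests, and say whether they use post-treatment values or reductions. Leave the chi-square tests of the 50% and 75% responder rates unchanged.
- **Allocation:** state how patients were assigned, since the gains above assume random assignment.

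The cost is small but not zero: one degree of freedom per model (about 0.9% of variance), reliance on a linear or log-linear form, possible slight excess type I error in the count model, and the need to define the baseline attack period, the week-4 time point and the count model. The document is written in the past tense; if outcomes have already been seen, the adjusted analyses must be labelled post hoc.
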